2.2.4 Study Drug

Study drug is administered only at clinical sites. All clinical sites must have the appropriate equipment and trained personnel needed to effectively manage hypersensitivity reactions including anaphylaxis and infusion reactions.

A brief description of study drug administration is listed below.

Cohort 1 MAU868 Arm:

- MAU868 1350 mg IV over at least 60 minutes approximately every 28 days for a total of 4 doses.

Cohort 2 MAU868 Arm:

- MAU868 6750 mg IV over at least 180 minutes on Study Day 1, then 1350 mg IV over at least 60 minutes for subsequent doses approximately every 28 days for a total of 4 doses.

Cohort 3 MAU868 Arm:

- MAU868 6750 mg IV over at least 180 minutes approximately every 28 days for a total of 4 doses.

Placebo

- Cohort 1: Placebo (D5W) will be administered as an IV infusion over at least 60 minutes approximately every 28 days for a total of 4 doses.
- Cohort 2: Placebo (D5W) will be administered as an IV infusion over at least 180 minutes on Day 1 and then over 60 minutes approximately every 28 days for a total of 4 infusions.
- Cohort 3: Placebo (D5W) will be administered as an IV infusion over at least 180 minutes approximately every 28 days for a total of 4 infusions.
- Placebo is prepared as a standard 250 mL volume of intravenous fluid.

All infusions will be followed by at least a 25 mL D5W flush to run at the same infusion rate as the dose of study drug.

Dose adjustments and interruptions of study drug are not permitted. Interruptions of individual infusions, however, are permitted in the event venous access becomes compromised or a subject is not tolerating the infusion. The details of any interruption of an infusion, including the reason(s), the timing, and the resumption and completion of the infusion if applicable, must be recorded in the source documents and the eCRF.

For subjects who may require a hemodialysis, plasmapheresis, or immunoabsorption treatment, it shall be assumed that the study drug has been removed. A blood sample for PK analysis should be collected prior to and following these treatments. In the event that a subject requires hemodialysis, plasmapheresis, or immunoabsorption treatments; if <15 days since last MAU868/placebo treatment another dose will be given as soon as possible, and the next scheduled monthly dose skipped. Regular dosing will occur the following month. If the last dose was 15 days or greater no interim dose will be administered, and the regular monthly schedule will be followed. No subject will receive more than 4 doses. Subjects anticipated to require hemodialysis, plasmapheresis or immunoabsorption treatment at the time of randomization should not be randomized.

2.2.5 Study Assessments

Table 1 illustrates the visit schedule and procedures of the study to be conducted at each visit.

TABLE 1: SCHEDULE OF EVENTS

	Pre-treatment ^{1,7}	Treatment Period ² (12 weeks)										Follow-up Period ³ (24 weeks)		
		Baseline	Tx1	Tx2	Tx3	Tx4	Tx5	Tx6	Tx7	Tx8	Tx9	FU1	FU2	FU3/ET
Visit Name	Screening	0	1	2	3	4	5	6	8	10	12	16	20	36
Study Weeks		0	1	2	3	4	5	6	8	10	12	16	20	36
Study Days	-10 to -1	1 ⁴	7	14	21	28	35	42	56	70	84	112	140	252
Informed consent	X													
I/E criteria	X	X												
Medical history	X													
KDPI ⁵	X													
Prior and concomitant medications ⁶	X	X	X	X	X	X	X	X	X	X	X	X	X	X
Demography	X													
Randomization ⁷		X												
Dose administration ^{4,8}		X				X			X		X			
Urine for BKV PCR and resistance testing ⁹		X ¹⁰	X	X	X	X	X	X	X	X	X	X	X	X
Plasma for BKV PCR and resistance testing ¹¹	X	X ¹⁰	X	X	X	X	X	X	X	X	X	X	X	X
PK sample ¹²		X ¹³	X	X	X	X ¹⁴			X ¹⁴		X ¹³	X	X	X
Anti-drug antibodies ¹⁰		X ¹⁰				X			X		X	X	X	X
Anti-donor antibodies ¹⁵														
Pregnancy test ¹⁶	X					X			X		X			X
Vital signs ¹⁷	X	X	X	X	X	X	X	X	X	X	X	X	X	X
Body height	X													
Body weight	X	X				X			X		X			X
Physical examination	X										X			X
ECG (12-lead) ¹⁸		X									X			X

	Pre-treatment ^{1,7}	Treatment Period ² (12 weeks)										Follow-up Period ³ (24 weeks)		
		Baseline	Tx1	Tx2	Tx3	Tx4	Tx5	Tx6	Tx7	Tx8	Tx9	FU1	FU2	FU3/ET
Visit Name	Screening	0	1	2	3	4	5	6	8	10	12	16	20	36
Study Weeks		1 ⁴	7	14	21	28	35	42	56	70	84	112	140	252
Study Days	-10 to -1													
Blood and urine for safety ¹⁹		X ¹⁰		X		X			X		X	X	X	X
Adverse events	X	X	X	X	X	X	X	X	X	X	X	X	X	X

BKV BK virus; PCR polymerase chain reaction; PK pharmacokinetic; ECG electrocardiogram

1. Protocol specific procedures should not be performed until the subject has consented to participation in the study. However, assessments and procedures performed as part of standard of care prior to informed consent, including determination of BK viral load in plasma may be used to qualify a subject for the study.
2. During the treatment period, subjects should be seen approximately every 7 days (+/-3 days) during the first 6 weeks and approximately every 14 days (+/-5 days) for the duration of treatment. Subjects may be seen more often at the Investigator's discretion. Visit dates are determined from the Baseline Visit.
3. During the follow-up period, if the subject cannot be seen on the precise protocol-defined study day, the acceptable visit window is +/-10 days.
4. Study Day 1 is the calendar day on which the first dose of study drug is administered. Subsequent study days are based on calendar days.
5. The information necessary for determining the KDPI includes *donor* age, height, weight, ethnicity, history of hypertension, history of diabetes mellitus, cause of death, serum creatinine, hepatitis C serostatus, and whether donation occurred after circulatory death.
6. Record any and all immunosuppressive medication from induction to randomization as well as any other medications taken during the 10 days prior to randomization.
7. Randomization should occur as soon as possible after confirmation of qualifying viremia but not more than 10 days after the qualifying sample was collected. Dosing of study drug should occur as soon as possible after randomization.
8. In the event that a subject requires hemodialysis, plasmapheresis, or immunoabsorption treatments; if <15 days since last MAU868/placebo treatment another dose will be given as soon as possible, and the next scheduled monthly dose skipped. Regular dosing will occur the following month. If the last dose was 15 days or greater no interim dose will be administered and the regular monthly scheduled will be followed. No subject will receive more than 4 doses.
9. A sufficient amount of urine should be collected at each assessment to accommodate three tests; one for BKV DNA PCR, one for possible genotypic resistance testing and a back up sample. Refer to the study's Laboratory Manual for volume requirements.
10. On Study Day 1 collect samples for BKV PCR, antidrug antibodies, and safety labs prior to administration of first dose of MAU868. Refer to the study's Laboratory Manual for collection requirements.
11. After screening, plasma samples should be collected and sent to the central laboratory at each assessment for BKV DNA PCR, possible genotypic resistance testing and a backup sample. During screening, only BKV PCR is required and may be performed by the laboratory used by the site for usual clinical care, or sent to the central lab for testing. Refer to the study's Laboratory Manual for volume requirements.
12. In the event subject undergoes hemodialysis, plasmapheresis, or immunoabsorption treatment, a PK sample should be collected prior to and following the respective treatment.

13. Three PK samples should be collected on Study Day 1 (first dose administration) and Study Day 84 (last dose administration) : within approximately 30 minutes prior to the start of the infusion, within approximately 30 minutes following the end of the infusion and between approximately 3-6 hours after the end of infusion.
14. On Study days 28 and 56 (2nd and 3rd dose administrations), two PK samples should be collected: within 30 minutes prior to the start of infusion and within 30 minutes following the end of infusion.
15. Any anti-donor antibodies collected by the site should be recorded in the eCRF, but collection is not mandatory.
16. Only for females of child-bearing potential. A negative urine or serum pregnancy test performed locally within 96 hours prior to Study Day 1 (Baseline). Local urine dipstick or serum pregnancy testing should be performed before infusions #2 on Day 28, #3 on Day 56 and #4 on Day 84.
17. Vital signs (temperature, blood pressure, heart rate, respiratory rate and oxygen saturation) should be obtained at each visit if the visit is in person. If the visit is not in person vital signs are not required. On drug infusion days, vitals should be taken within 30 minutes before starting the infusion, and then approximately every 30 minutes (+/- 10 minutes) after the start of the infusion until at least 2 hours after completing the infusion.
18. ECGs should be performed prior to dose administration on Study Day 1 and after dose administration on Study Day 84 and on Day 252 (or at the Early Termination Visit)
19. Blood and urine for safety should be collected and sent to the central laboratory. Laboratory tests used in for the management and monitoring of the subject per standard practice may be performed at the local laboratory at the Investigator's discretion.

3 SAMPLE SIZE DETERMINATION

This study will randomize approximately 36 subjects (12 per cohort) to MAU868 and placebo in a 2:1 ratio (24 MAU868 and 12 placebo; 8 MAU868 and 4 placebo per cohort). This study is not powered to an efficacy endpoint. The number of subjects chosen will provide data useful in determining proof of concept.

4 DATA SAFETY MONITORING BOARD (DSMB)

An independent DSMB will review cumulative unblinded safety data as outlined in the DSMB charter. The DSMB will advise the Sponsor on the continuing safety of the study patients and those yet to be recruited to the study, as well as the continuing validity and scientific merit of the study. At any time, the DSMB may temporarily suspend enrollment until any significant safety concerns are resolved or terminate the study to ensure patient safety, if in the opinion of the DSMB, further dosing would pose an inappropriate safety risk.

5 SPONSOR STUDY REVIEW COMMITTEE (SSRC)

The SSRC includes a Sponsor medical representative, the Medical Monitor and a selected site Principal Investigator acting as the SSRC Chair. Approximately 12 weeks after the 9th subject in Cohort 1 has been randomized, blinded safety data will be reviewed by the SSRC to determine progression from Cohort 1 to Cohort 2. Cohort 3 will not be opened for screening and enrollment until an evaluation of unblinded safety, efficacy and pharmacokinetics findings from both Cohorts 1 and 2 through the 12-week treatment period has been completed by the SSRC.

The SSRC may recommend enrolling more than 12 subjects into a cohort (Cohort 1, 2, and/or 3) to allow adequate data collection for assessment of cohort progression and/or study objectives. Expansion of a given cohort, if needed, will not affect the size of subsequent cohort(s).

In addition, a first interim analysis on unblinded safety and tolerability data, efficacy data will be reviewed by the SSRC once all 12 subjects in Cohort 1 have completed the treatment period. Unless a significant safety issue related to administration of MAU868 has been identified, the conclusions will have no impact on Cohort 2 or the study's design.

Following completion of the 12-week treatment periods for Cohorts 1 and 2, a second interim analysis on cumulative unblinded data from both cohorts will be reviewed for safety and tolerability, efficacy and PK. Based on the SSRC's safety, efficacy and PK conclusions for Cohorts 1 and 2, the dosing regimen for Cohort 3 may be adjusted in dosage and/or duration; however, the dosage and duration for Cohort 3 will not exceed the dose already specified in the protocol.

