4.3 Treatment Arm Blinding

This is a subject, Investigator, and Sponsor-blinded study. Subjects and Investigators will remain blinded to study treatment arm (MAU868 or placebo) throughout the study.

Drug product will be supplied in bulk, so an unblinded pharmacist, or appropriately designated study site staff who is independent of the study team, will be required in order to maintain the blind. This unblinded associate at the site will be notified by the IWRS that a subject is randomized and to which treatment arm, which will then enable and instruct them to prepare the study drug.

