Prior medications are medications used before the first dose of study drug. Concomitant medications are medications that were taken on or after first dose of study drug. Any medications used before first dose of study drug and continued will be counted as both prior and concomitant medications.

The number and percentages of patients who receive the following prior and concomitant medications will be summarized by ATC class and preferred term based on ITT, MITT, and Safety Populations:

- Prior medications;
- Concomitant medications;
- Prior immunosuppressive agents with dose decreased or discontinued due to BKV;
- Concomitant immunosuppressive agents with dose decreased or discontinued due to BKV;
- Prior immunosuppressive agents with clinically significant decrease in dose or discontinuation;
- Concomitant immunosuppressive agents with clinically significant decrease in dose or discontinuation.

All prior and concomitant medications will be listed by treatment and subjects.

Any clinically significant (based on blinded review of medical monitor) decrease in dose or discontinuation of prior or concomitant immunosuppressive medication will be described regardless of whether the reason was due to BKV or not.

7.3.6 *Study Drug Exposure*

All study drug will be administered by IV infusion. Days of exposure to study drug will be calculated as the last dose date of study drug – first dose date of study drug + 1. The days of exposure to study drug will be summarized based on the Safety and MITT Populations with

descriptive statistics and with counts and percentages of subjects with exposure in the following categories:

- ≤ 28 days
- >28 to ≤ 56 days
- >56 to ≤ 84 days
- >84 days

Total number of doses received will be summarized based on the Safety and MITT Populations with counts and percentages of subjects in the following categories: 1, 2, 3, and 4 doses.

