8 INTERIM ANALYSIS

8.1 First Interim Analysis

Following completion of the 12-week treatment period of Cohort 1, unblinded safety and tolerability data (adverse events, clinical laboratories, vitals/physical exams and ECGs), efficacy data (BKV viral load in the plasma) and PK (MAU868 plasma levels) will be provided in the form of individual subject case data packages and reviewed by the SSRC. The treatment assignment in Cohort 1 will be unblinded; however, these data will not include associated subject or site identifiers. The objectives of this interim analysis/this data review are to evaluate whether four doses MAU868 1350 mg IV administered every 28 days for a total of 4 doses demonstrate:

- safety and tolerability signals compared to placebo
- a decrease in BK plasma viral load compared to placebo
- predicted MAU868 plasma levels

The conclusions from this first interim analysis will be used by the Sponsor to evaluate the safety and efficacy of MAU868 early-on in this first-in-patient study. Unless a significant safety issue related to administration of MAU868 has been identified, the conclusions will have no impact on Cohort 2 or the study's design.

For the first interim analysis, unblinded programmed patient profiles will be provided.

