8.2 Second Interim Analysis

Following completion of the 12-week treatment periods for Cohorts 1 and 2, cumulative unblinded programmed data from both cohorts will be reviewed for safety and tolerability (adverse events, clinical laboratories, vitals/physical exams and ECGs), efficacy (BKV viral load in the plasma) and PK (MAU868 plasma levels). The objectives of this second interim analysis are to evaluate whether four doses MAU868 1350 mg IV administered every 28 days for a total of 4 doses or MAU868 6750 mg IV administered as a first dose followed by 3 more doses of MAU868 1350 mg IV administered every 28 days demonstrate:

- safety and tolerability signals compared to placebo
- a decrease in viral load compared to placebo

- predicted MAU868 plasma levels

Based on the SSRC's assessment of safety and tolerability and the sponsor assessment of the safety and tolerability, efficacy and PK conclusions for Cohorts 1 and 2, the dosing regimen for Cohort 3 may be adjusted in dosage and/or duration; however, the dosage and duration for Cohort 3 will not exceed the dose already specified in the protocol. Cohort 3 will not be opened for screening and enrollment this evaluation has been completed.

For the second interim analysis, cumulative unblinded programmed patient profiles will be provided. In addition, the programmed statistical tables and listings for Cohorts 1 and 2 will be presented.

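### The Medical Monitor and one site investigator see unblinded individual profiles as SSRC members, so the blinded judgements in SAP 7.3.5 and the unqualified investigator blind are not assured for Cohorts 1 and 2

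*SAP*

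**What the plan says.** On the blind, Protocol 4.3 describes a study blinded to subject, investigator and sponsor, and adds: "Subjects and Investigators will remain blinded to study treatment arm (MAU868 or placebo) throughout the study". SAP 2.2.2 repeats both statements. Neither section makes an exception for committee members.

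On the committee, SAP 5 says: "The SSRC includes a Sponsor medical representative, the Medical Monitor and a selected site Principal Investigator acting as the SSRC Chair". Protocol 3.1 lists the same three roles.

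On what the committee sees, SAP 8.1 says that Cohort 1 data after the 12-week treatment period "will be provided in the form of individual subject case data packages and reviewed by the SSRC", and then: "For the first interim analysis, unblinded programmed patient profiles will be provided". SAP 8.2 says: "For the second interim analysis, cumulative unblinded programmed patient profiles will be provided". It adds programmed tables and listings, and SAP 8.2.1 includes concomitant procedures and medications among the material the SSRC assesses.

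On safeguards, SAP 8.1 says: "The treatment assignment in Cohort 1 will be unblinded; however, these data will not include associated subject or site identifiers". Protocol 10.8.6 makes the same provision for both interims. SAP 8.2 does not repeat it.

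On judgements that depend on a blind, SAP 7.3.5 reports clinically significant reductions or discontinuations of immunosuppression "based on blinded review of medical monitor". SAP 7.5.1.9 lets SSRC opinion decide which biopsy-proven BKV nephropathy cases are left out of the summary, and states no blinding for that decision.

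**The concern.** Reducing immunosuppression is the guideline response to BK viremia (Protocol 1.1), so it is the main competing explanation for a fall in viral load. The SAP 7.3.5 classification is how a reader would check that explanation, and its value depends on the classifier not knowing the arm. The named classifier sits on the committee that receives arm-labelled profiles. At the second interim that committee also reviews the concomitant-medication data to be classified.

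The nephropathy exclusion raises the same issue with more at stake. BKV nephropathy is compared between arms by logistic regression and Fisher's exact test at Weeks 12, 16 and 36. A committee that may know the arms decides which cases leave the summary. Biopsies are not mandated (Protocol 8.4), so an unblinded site investigator could also be influenced in decisions about own-site subjects.

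**Working it through.** No sample size or error rate is in dispute. The check is who sees what and when, and how far removing identifiers protects the blind.

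**Counts.** Inputs are three cohorts of 8 active and 4 placebo (SAP 3). This reproduces the plan's total: 3 × (8 + 4) = 36, with 24 active and 12 placebo.
- After interim 1: 12/36 = 33% have been seen as unblinded profiles.
- After interim 2: 24/36 = 67% (16 active, 8 placebo).
- Cohort 3 (12 subjects) is in neither interim.

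**Follow-up still open.** Treatment visits end at Day 84 and follow-up at Day 252 (schedule of events). The last subject to finish treatment has 252 − 84 = 168 days, or 24 weeks, left. That is the maximum. Let t1 and t2 be the weeks of the last Cohort 1 and last Cohort 2 randomizations. Interim 2 falls no earlier than t2 + 12, and Cohort 1 completes Week 36 at t1 + 36. Cohort 1 has therefore finished by interim 2 whenever t2 − t1 ≥ 24. The documents give no accrual rate, so 67% with follow-up pending is an upper bound.

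**Who could match a profile.** Matching needs identified data from elsewhere. Protocol 8.3 reports each subject's central PCR results to the investigator, so the SSRC investigator holds identified viral loads for own-site subjects. With about 20 sites that averages 12/20 = 0.6 subjects in Cohort 1 and 24/20 = 1.2 in Cohorts 1 and 2. That the Medical Monitor sees identified data on all subjects is inferred from the role (for example, the unblinding consultations in Protocol 4.3.1). The documents do not state it.

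**Could a viral-load series single out a subject?** The schedule has 10 plasma samples from Day 1 to Day 84. Assume that values are read in equal cells over 10^3 to 10^7 copies/mL (the eligibility limits), equally likely and independent. Over v visits, K = cells^v. The chance that a given subject's series is unique among m profiles is (1 − 1/K)^(m − 1). For 40 cells, two visits and m = 12: K = 1,600 and (1 − 1/1,600)^11 = 0.993.

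| Reading | Visits | Among 12 | Among 24 |
|---|---|---|---|
| Half-log (8 cells) | 1 | 0.23 | 0.05 |
| Half-log | 2 | 0.84 | 0.70 |
| Half-log | 3 | 0.98 | 0.96 |
| 0.1 log (40 cells) | 1 | 0.76 | 0.56 |
| 0.1 log | 2 | 0.993 | 0.986 |
| 0.1 log | 3 | 0.9998 | 0.9996 |

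Real values are correlated within a subject, so these are illustrative upper-end figures. Labs and adverse events in the profiles add matching information.

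**Timing of the blinded tasks.** Neither document says when the SAP 7.3.5 review or the SAP 7.5.1.9 exclusions take place relative to the interims, or assigns either to someone without access.

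**The case against.** The strongest reply is that removing identifiers is a real safeguard, and that a Medical Monitor review completed before each interim would satisfy SAP 7.3.5 as written. Protocol 10.5.1 also defers interim details to an SSRC Charter, which is not among the documents and may contain controls. This stands to the extent that no failure of the blind is shown. It does not close the gap. A charter cannot correct the absolute statement in Protocol 4.3 and SAP 2.2.2, and the SAP sets no order of events.

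The second reply is that the effect on results is small. Much of this stands. Plasma viral load is a central-laboratory PCR result. Each interim follows the treatment period, so Week 1 to 12 values for the unblinded cohorts are already collected. The SAP 7.3.5 judgement feeds descriptive tables and enters no model in SAP 7.5.1, and all medications are listed by subject, so a reader can reclassify.

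The third reply is that sponsor access at the interims is openly planned. SAP 8.2 even names "the sponsor assessment of the safety and tolerability, efficacy and PK conclusions" as an input to the Cohort 3 regimen, and the blind that is stated to last throughout covers only subjects and investigators. That is fair. The sponsor representative's access needs disclosure in the blinding section, but it is not the main point.

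A reader might infer that the blind simply does not hold, or that so few subjects per site makes every profile easy to match. The documents support neither. Site identifiers are removed, and a low count per site means that the one SSRC investigator has few own-site subjects to recognize. The other profiles are of patients whom that investigator does not treat.

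**Conclusion.** The point holds as a gap in assurance. For Cohorts 1 and 2, the plan does not ensure that the Medical Monitor is blinded when classifying immunosuppression changes, or that all investigators stay blinded throughout. The exposure is at most 12 of 36 subjects after interim 1 and 24 of 36 after interim 2, assuming no cohort is expanded beyond 12. Up to 24 weeks of follow-up remain for the last subjects to finish treatment.

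The direct consequence for SAP 7.3.5 is limited because its output is descriptive. The nephropathy exclusion in SAP 7.5.1.9 matters more, because the endpoint is tested at Weeks 12, 16 and 36. The SAP does not say whether an exclusion from the summary carries into those tests. Cohort 3 judgements are unaffected by these two interims.

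The conclusion assumes that profiles show serial viral loads, labs and adverse events, as SAP 8.1 and 8.2 describe, and that the SSRC Charter does not already fix the timing.

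**What to change.** 1. In SAP 7.3.5, require the Medical Monitor's classification of treatment-period changes to be completed and locked for each cohort before that cohort is unblinded. Classify changes in later follow-up by a rule written before unblinding. Apply the same lock or pre-written rule to the exclusions in SAP 7.5.1.9.
2. In SAP 8.2, repeat that no subject or site identifiers accompany the unblinded data, and apply this to profiles and listings.
3. In Protocol 4.3 and SAP 2.2.2, state which SSRC members are unblinded, to which cohorts, and when.

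The cost is an earlier data-review step before each interim, plus wording. No test or sample size changes. I would not ask the Medical Monitor and the site investigator to leave the unblinded session or see only arm-level tables. The SSRC has three listed members, so that would leave the sponsor representative alone with the individual data on which the Cohort 3 decision rests. Interim 1 as planned provides profiles only, so arm-level tables would also need new programming.
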